a) Serotonin Syndrome or Neuroleptic Malignant Syndrome (NMS) like Reactions: Although lorcaserin has not been associated with any known cases of either serotonin syndrome or NMS, the safety of co-administration of lorcaserin with other serotonergic or anti-dopaminergic agents has not been established.

b) Cardiac valvular and conduction abnormalities: Asymptomatic aortic or mitral regurgitations were seen in patients who were in a randomized control trial of lorcaserin vs placebo for a one-year period, likely due to long-term activation of serotonin receptors on cardiac interstitial cells. In a similar year-long trial of lorcaserin vs placebo, some patients experienced a decrease in their heart rate over time.

c) Cognitive Impairment and Depression or suicidal thoughts: in trials of at least 1 year duration, lorcaserin administration was associated with difficulty with concentration and attention, difficulty with memory and confusion, and some mood problems such as depression.

d) Psychiatric Disorders (including euphoria and dissociation): have been associated with short-term studies of lorcaserin at supratherapeutic dosages.

e) Hypoglycemia was observed in some participants with Type 2 Diabetes on lorcaserin while concomitantly on a sulfonylurea.

f) Priapism: Although lorcaserin has not been associated with cases of priapism, serotonergic drugs like lorcaserin have been associated with priapism.

2) Risk of stopping/adjusting other medications: There may be risks associated with the temporary stopping of other medications

3) EMG and Nerve Conduction Studies: Participants may experience some discomfort. There might also be some bruising in the area where the wire is inserted. Most subjects will not experience any bleeding with the needle studies; even for patients receiving therapeutic anticoagulation, the reported risk of clinically silent hematoma formation is less than 2% (30). If bleeding occurs, no more than a few drops is expected. The risk of infection is extremely small.

4) Blood sampling: Participants may experience discomfort, bruising or bleeding at the site of blood draws. All patients will have blood drawn for research purposes either through indwelling catheters or percutaneously by either a licensed clinical staff or trained research personnel. Risks of percutaneous blood draws are uncommon and include bleeding, discomfort and bruising.

5) Chart Abstraction: There is a risk of loss of privacy, since we will be collected data on participants.

6) Strength testing: Participants may feel some tiredness or discomfort in the arm and leg muscles

7) Questions: There is a small chance that a participant could become uncomfortable, bored or fatigued in answering our questions.

8-b) Steps taken to minimize the risks.

1) Side effects of drug/placebo

a) Serotonin Syndrome and NMS-like reactions:

Although this syndrome is rare, the theoretical risk of serotonin syndrome and NMS-like reactions will be mitigated by

- i. Monitoring participants for liver and renal failure, which may affect drug levels
- ii. Reviewing medication lists to exclude patients on drugs that may cause serotonin syndrome when administered along with lorcaserin (see Appendix A and section 4-d above).
- iii. Allowing participants to be on no more than 1 serotonergic agent (plus lorcaserin/placebo) during the trial.
- iv. Closely monitoring patients, for toxicity using the NPI-C for mental status changes and Hunter Criteria for Serotonin toxicity.

b) Cardiac valvular and conduction abnormalities:

Patients with a history of valvular heart disease, bradycardia, and 2nd or 3rd degree AV block without pacemaker will be excluded. Participants are unlikely to develop new onset valvular defects given that they will only receive two doses in this trial. Participants will be closely monitored via EKG for bradycardia and new onset 2nd or 3rd degree AV block.

c) Cognitive impairment, Psychiatric Disorders (including euphoria and dissociation) and Depression:

Patients with pre-existing cognitive impairment and psychosis will be excluded. During the trial, patients will be closely monitored using the RASS, CAM-ICU and NPS (Neuropsychiatric screening) instruments.

d) Hypoglycemia: Patients will be excluded if they are receiving a sulfonylurea medication at the time of the study

e) Priapism: this is a theoretical risk will be mitigated by excluding patients with a prior history of priapism, and monitoring during the trial via any noted side effect.

2) Risks of stopping/adjusting other medications: These risks will be assessed on a case-by-case basis, in consultation with the participants' medical team.

3) EMG and Nerve Conduction Studies: This is an abbreviated version of a clinical test routinely done, including in the critical care setting. The discomfort to participants is very brief and will not persist beyond the end of this short screening test. The risks of bleeding and infection will be minimized even further by using single-use, small needles, cleaning the area of insertion, and avoiding needle insertion in areas of untreated infection.

4) Blood sampling: Person(s) collecting blood samples will be trained to minimize avoidable discomfort, bruising and bleeding. Most blood will be drawn through indwelling catheters and most of the routine lab work required for this study will already be drawn as part of routine care with little, if any, additional lab work required for this study.

5) Protection of Privacy:

All patient data will be confidential and secure due to physical and electronic data security measures, including locked offices and locked filing cabinets for records and computers, and password protection for computers and electronic data storage. All electronic data will be routinely backed up. Only study staff that are directly involved in data entry, management, or processing, will know the linkage between the unique identifier and participant-identifying information. We will keep all patient information confidential in accordance with Public Health Services Act (42 USC 299a-1(c)).

6) Muscle Strength Testing: We will minimize discomfort of strength testing by monitoring patients and assuring that pre-existing pain is treated before study procedures, by positioning carefully, and by allowing the option to cancel or postpone any assessment, either by subject request or clinical condition.

7) Recruitment and Informed Consent

An informed consent process, consistent with the IRB policies and procedures, will be used to enroll each patient for this proposed investigation. It will be emphasized that participation is entirely voluntary and may be discontinued at any time without any impact on the care received during his/her hospital stay. Consent will be documented in writing on an IRB-approved consent form and entered into the medical record, to ensure all ICU providers and nursing staff are aware of the patient's participation.

8-c) Plan for reporting unanticipated problems or study deviations.

The primary investigator ([name]) is a board-certificated critical care physician practicing in the intensive care unit at Johns Hopkins. He will be involved in the daily conduct of the clinical trial and closely supervise the daily screening for patient eligibility, informed consent, and study procedures such outcomes assessments and safety monitoring during the trial. Consequently, immediate knowledge of any unanticipated problem or study deviation that may arise will be available to the P.I. ([name]) on a timely basis for immediate action and reporting to the IRB as necessary. If [name] is unavailable, the study will maintain a list of clinicians associated with the study and [name] research group who can provide medical guidance.

Administration of lorcaserin/Placebo will be done by licensed clinical staff in coordination with the research pharmacy.

Examples of events that are anticipated in this population of critically ill patients include: transient hypoxemia and hypotension, agitation, delirium, skin breakdown, nosocomial infections, glucose dysregulation, deep venous thrombosis/pulmonary embolus, tube feeding intolerance, cardiovascular compromise, end organ compromise or failure (e.g. renal failure) and death. These events and other similar events, which are often the focus of prevention efforts as part of routine ICU care, will not be considered reportable adverse events unless they are considered by [name] to be associated with the study protocol. Serious adverse events are defined any untoward clinical events that are:

- Fatal or immediately life threatening
- Permanently disabling or severely incapacitating
- Requires prolonged inpatient hospitalization
- Important medical events that may not result in death, be life threatening, or require prolonged hospitalization may be considered serious adverse events when, based on appropriate medical judgment, they may jeopardize the patient and may require medical or surgical intervention to prevent one of the serious outcomes listed above.

If clinically important, unanticipated adverse problems or clinically important study-related, serious adverse events occur, they will be recorded on a designated case report form. All events that are serious and unanticipated, or study-related and adverse will be reported to Institutional Review Board within the required reporting timeline.

8-c) Legal risks such as the risks that would be associated with breach of confidentiality.

All patient data will be confidential and secure due to physical and electronic data security measures, including locked offices and locked filing cabinets for records and computers, and password protection for computers

Date: 1 August 2016

Principal Investigator: [name] PhD

Application Number: IRB00072940

and electronic data storage. All participant-identifying information will be removed from the dataset before analysis. Only study staff who are required to, will know the linkage between the unique identifier and participant-identifying information. We will keep all patient information confidential in accordance with Public Health Services Act (42 USC 299a-1(c)). There is low risk of a breach of confidentiality.

8-d) Financial risks to the participants.

There are no expected financial risks to the participants

9) Benefits

9-a) Description of the probable benefits for the participant and for society.

There is no direct benefit to participants in this study.

If this trial yields encouraging preliminary data, this would encourage further prospective assessments of lorcaserin using repeat dosing, to establish repeat dosing safety in the ICU and efficacy (i.e., improvement in muscle strength) in critically ill patients with sepsis.

Demonstration of lorcaserin efficacy could result in the first specific drug therapy treating muscle weakness in critically ill ICU patients. Expediting the physical recovery of these patients early in their ICU course has the potential to improve rehabilitation after critical illness. Possible patient benefits could include reduced hospital stays and improved functional outcome. Since lorcaserin is already FDA-approved and on the market with an excellent safety profile (29), success in identifying a biological effect of lorcaserin to improve motor unit function in ICU patients may make translation of these findings into ICU practice more feasible.

10) Payment and Remuneration

10-a) Detail compensation for participants including possible total compensation, proposed bonus, and any proposed reductions or penalties for not completing the protocol.

Participants will not be paid for participating in this study.

11) Costs

11-a) Detail costs of study procedure(s) or drug (s) or substance(s) to participants and identify who will pay for them.

There will not be any additional costs to participants beyond routine financial obligations for their hospitalization.

12) Appendices

12-A) Appendix A – List of drugs that if currently administered, will result in exclusion of the participant (details in Section 4-d of eFormA).(31-34). Basis of the exclusion (i.e., either serotonin interaction or CYP2D6 interaction) is indicated.

GENERIC NAME	COMMON NAME	CLASS/GROUP	USE	Serotonin Interaction	CYP2D6 Interaction	NOTES
5-hydroxytryptophan	Oxitriptan / 5-HTP	OTC supplement of a naturally occurring amino acid	Sleep aid - anti depression	Yes		OTC. The interaction reports apply to the OTC supplement form.
Amitriptyline (> 50 mg/day)		TCA		Yes	Yes	
Amphetamine		Stimulant	ADHD - narcolepsy	Yes		
Aripiprazole		Atypical antipsychotic	Psychosis		Yes	
Atomoxetine	Strattera	Norepinephrine reuptake inhibitor	ADHD		Yes	
Brompheniramine		Antihistamine	Common cold and allergic rhinitis	Yes		OTC
Bupropion	Wellbutrin	Aminoketone	Antidepressant	Yes	Yes	
Carvedilol		Beta blocker	CHF-HTN		Yes	
Clomipramine	Anafranil, clofranil	TCA		Yes	Yes	
Clorgiline		Irreversible MAO-A inhibitor	Scientific research	Yes		
Cyclobenzaprine	Amrix, Flexeril, Fexmid		Muscle relaxer	Yes		
Desipramine	Desmethylimipramine	TCA		Yes	Yes	
Dextromethorphan		Morphinan	Cough suppressant	Yes	Yes	Ingredient in many OTCs
Doxepin	Deptran, sinequan	TCA		Yes	Yes	
Flecainide	Tambocor	Class Ic antiarrhythmic	Tachyarrhythmia		Yes	
Fluoxetine		SSRI		Yes	Yes	
Furazolidone		Antibacterial		Yes		
Ginseng		Plant	Energy drinks - herbal teas	Yes		
Hypericum perforatum	St. John's wort	Plant	Herbal treatment for depression	Yes		
Imipramine		TCA		Yes	Yes	
Isocarboxazid		Irreversible MAO inhibitor	Mood disorders	Yes		
Linezolid	Zyvox	Antibiotic		Yes		
Lofepramine		TCA	Antidepressant	Yes		
L-tryptophan	Dietary supplement	One of the 22 standard AA essential AA in human diet	Dietary supplement	Yes		OTC. The interaction reports apply to the OTC supplement form.
Methadone		Opioid	Analgesic - maintenance anti-addictive	Yes		
Metoclopramide		Dopamine-receptor antagonists	Treat nausea and vomiting	Yes		
Mexiletine	Mexitol	Class Ib anti-arrhythmic			Yes	
Moclobemide		Reversible MAO-I		Yes		Not USA approved yet
Nortriptyline		TCA	Depression - nocturnal enuresis - chronic pain	Yes		

Date: 1 August 2016

Principal Investigator: [name] PhD

Application Number: IRB00072940

Paroxetine		SSRI		Yes	Yes	
Peganum harmala	Esfand, Syrian rue, harmel	Plant		Yes		
Pentazocine		Mixed agonist-antagonist narcotic	Analgesic	Yes		
Phenelzine		MAO-I	Antidepressant	Yes		
Procarbazine		Antineoplastic chemotherapy drug	Hodgkin's lymphoma	Yes		
Propoxyphene		Opioid	Analgesic	Yes		
Ritonavir	Norvir	Protease inhibitor	HIV/Aids	Yes		
Selegiline		Irreversible MAO-I	Parkinson/depression/dementia	Yes		
S-metoprolol		Beta blocker			Yes	
Tamoxifen		Agonist-antagonist estrogen	Cancer		Yes	
Thioridazine		Typical antipsychotic			Yes	
Timolol		Beta-adrenergic receptor antagonist	Glaucoma - HTN - Migraine		Yes	
Tramadol	Ultram	Opioid	Pain	Yes	Yes	
Tranylcypromine	Parnate	Irreversible MAO-I	Depression - anxiety	Yes		

12-B) Appendix B – List of drugs that if currently administered, will require physician approval for participant to be included in the study (details in Section 4-d of eFormA).(31-34)

GENERIC NAME	COMMON NAME	CLASS/GROUP	USE	Serotonin Interaction	CYP2D6 Interaction	NOTES
Codeine	3-methylmorphine	Opiate	Analgesic		Yes	
Duloxetine	Cymbalta	SNRI	MDD - GAD	Yes	Yes	
Haloperidol	Haldol	Typical antipsychotic			Yes	
Risperidone		Atypical antipsychotic			Yes	
Venlafaxine	Effexor	SNRI		Yes	Yes	
Amitriptyline (≤ 50 mg/Day)		TCA		Yes	Yes	
Bromocriptine	Parlodel, Cycloset	Ergoline Derivative - Dopamine agonist	Pituitary tumors - Parkinson's - Hyperprolactinemia - NMS	Yes		
Buspirone	Buspar	Azapirone	anxiolytic	Yes		
Carbamazepine			Anticonvulsant	Yes		
Chlorphenamine	Chlorpheniramine, piriton	Antihistamine	Allergies	Yes		
Citalopram	Celexa, cipramil	SSRI		Yes		
Dextropropoxyphene		Opioid	Analgesic	Yes		
Escitalopram	Lexapro, cipralex	SSRI		Yes		
Fentanyl	Fentanil	Opioid	Analgesic	Yes		Including the patch (Duragesic)
Fluvoxamine		SSRI		Yes		
Granisetron	Kytril	Antiemetic	After chemo	Yes		
Lithium		Element	Bipolar disorder	Yes		
Meperidine	Pethidine	Opioid	Analgesic	Yes		

Date: 1 August 2016

Principal Investigator: [name] PhD

Application Number: IRB00072940

Milnacipran	Ixel, savella, dalcipran, toledomin	SNRI	Fibromyalgia	Yes		
Mirtazapine		NaSSA	Antidepressant	Yes		
Nefazodone	Dutonin, nefadar, serzone	SNDRI	Antidepressant	Yes		
Sertraline		SSRI		Yes		
Tapentadol	Nucynta	Opioid	Analgesic	Yes		
Toloxatone	Humoryl	Antidepressant		Yes		
Trazodone		Serotonin antagonist and reuptake inhibitor	Antidepressant	Yes		
Triptans (controversial)	Sumatriptan, rizatriptan, naratriptan, eletriptan, almotriptan, frovatriptan, avitriptan, zolmitriptan			Yes		
Valproate	Valproic acid	Anticonvulsant	Anticonvulsant/mood stabilizer	Yes		
Ondansetron	Zofran	Serotonin 5-HTa receptor antagonist	Antiemetic	Yes	Yes (minor)	

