Patient Risk Factors	Method for data collection	Measurement Scale
Age/sex/race/ethnicity	Chart review	Continuous/Binary/Categorical
Weight/Height	Chart review	Continuous
Comorbidities: Charlson* & Functional Indices**	Chart review	Ordinal
Severity of illness: APACHE II***	Chart review	Continuous
Leg/Hand dominance	Patient/Proxy interview	Binary
Past Psychiatric History***	Chart review	Categorical

*Charlson Comorbidity index: a score derived from 19 categories of comorbidities, with an increased score reflecting an increased likelihood of one-year mortality(20).

**Functional Comorbidity Index: An 18 item list of diagnoses which uses physical function as the outcome of interest, with increased score indicative of decreased function(21).

Date: 1 August 2016

Principal Investigator: [name] PhD

Application Number: IRB00072940

****Acute Physiology and Chronic Health Evaluation (APACHE II): An index of disease severity that takes into account age, pre-existing medical conditions, and 12 acute physiologic variables that are assessed during the first 24 hours of ICU admission. Scored on a scale from 0-71, with higher scores indicating more severe disease and increased mortality risk(22).*

Table 2: Potential confounders – ICU status

ICU exposure risk factors	Method of Data Collection	Measurement Scale
Sequential Organ Failure Assessment (SOFA) Score**	Chart review	Continuous
ICU admission diagnosis details	Chart review	Categorical

** *SOFA: A composite score that takes into account 6 organ systems used to assess the severity of organ dysfunction in ICU(23), collected on Days 1 and 3.*

4-a-5) Sequence and Timing of Study Events

On Day 1, intervention and control group participants receive 10 mg of lorcaserin or placebo, respectively. Both groups also will undergo assessments before and after administration of lorcaserin/placebo (for assessment details and times, see table 3 and section 4-a-6)

On Day 2, the intervention and control group participants will not receive any lorcaserin/placebo, but will undergo repeat assessments (for assessment details and times, see table 3 and section 4-a-6)

On Day 3, the intervention and control group participants receive 30 mg of lorcaserin or placebo, respectively. Both groups also will undergo assessments before and after administration of lorcaserin/placebo (identical to Day 1).

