On Day 4, the intervention and control group participants will not receive any lorcaserin/placebo, but will undergo assessments (identical to Day 2).

4-a-6) Measurements

Participants will be monitored to ensure safety of lorcaserin/placebo administration. This monitoring will include a daily review of interim history (via chart review), medications, and laboratory values (details below), as well as assessment for changes in mental status and monitoring for serotonin syndrome (see table 3).

We also will obtain a battery of outcome measures to test the efficacy in improving muscle strength and assess the safety of lorcaserin, as described in tables 3.

All monitoring will be done by assessors blinded to group allocation.

Table 3: Safety and Efficacy Measures (numbers indicate the number of times within each study day that each measurement is performed)

Measurement	Number of assessments			
	Day 1*	Day 2†	Day 3***‡	Day 4†
Safety Measures				
Chart Review	1	1	1	1
Laboratory Tests (details below)	1	1	1	1
EKG	2	1	1	1
RASS sedation score	2***	1	2***	1
CAM-ICU delirium screen	2***	1	2***	1
Neuro Psychiatric Screen	2	1	1	1
Hunter Serotonin Toxicity Criteria	1	1	1	1

Efficacy Measures				
Handgrip Strength (Primary Outcome)	2***	1	2***	1
Arm & leg strength (MMT using MRC Scale)	2***	1	2***	1
Quadriceps Strength using handheld dynamometry	2***	1	2***	1
Lorcaserin serum drug levels [‡]	1	1	1	1
Electromyography & Nerve Conduction Study	once only to assess for any peripheral neuromyopathy****			

MMT: Manual muscle strength testing; MRC: Medical Research Council; HHD: Hand-Held Dynamometry; EKG: Electrocardiogram; RASS: Richmond Agitation Sedation Scale; NPI-C: Neuropsychiatric Inventory - Clinician Rating Scale; CAM-ICU: Confusion Assessment Method for the ICU; Hunter Criteria: will be used to evaluate patients for serotonin syndrome (24)

* 10 mg of lorcaserin or placebo administered

** 30 mg of lorcaserin or placebo administered

*** measures are performed as close to the time as drug or placebo administration as possible (within 4 hours) and as soon as possible (between 2 - 6 hours) after drug or placebo administration, on Days 1 and 3 only

**** EMG & NCS will be performed at any time point after the patient is randomized into study, and will be used to help interpret the results of strength tests

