‡ Peak concentration serum samples will be collected 2 hours ± 15 minutes or 3 hours ± 15 minutes after drug administration (see section 4-a-6.11 for details) and trough concentration serum samples will be collected 24 hour ± 30 minutes after drug administration (see section 4-a-6.11 for details)

† Days 2 and 4 are consecutive to days 1 and 3 respectively.

‡ Day 3 may or may not be consecutive to day 2 depending on assessor availability.

Safety Measures

4-a-6.1) *Chart Review*: A daily review of participants' medical records for interim medical history and medications will be performed to monitor for any safety issues and ensure that participants continue to meet eligibility and safety criteria (see sections 5 and 4-f respectively).

4-a-6.2) *Laboratory Tests*: As indicated in table 3 above, participants will undergo daily blood draws for the following standard laboratory tests: Heme 8 and CMP. In particular, laboratory tests will be obtained prior to every dose of lorcaserin or placebo to ensure that patients meet eligibility and safety criteria (see sections 5 and 4-f respectively). If the relevant tests have already been done for clinical purposes, they will NOT be repeated for research purposes. As these labs are typically measured, at least daily, in the ICU setting, they may not need to be drawn for research purposes and the pre-existing values will be reviewed for research purposes.

4-a-6.3) *EKG*: Daily EKGs will be obtained to determine if participants develop bradycardia, new-onset QT prolongation (as defined in Section 4.f.3.4 below) or new 2nd or 3rd degree AV block. In particular, this test will be obtained prior to every dose of lorcaserin or placebo to ensure that patients meet eligibility and safety criteria (see sections 5 and 4-f respectively). If this test has already been done for clinical purposes, it will NOT be repeated for research purposes. As this test is commonly done, at least daily, in the ICU setting, it may not need to be done for research purposes and the pre-existing test will be reviewed for research purposes.

Date: 1 August 2016

Principal Investigator: [name] PhD

Application Number: IRB00072940

4-a-6.4) Richmond Agitation Sedation Scale (RASS)(25): is a validated instrument to measure agitation and sedation status in ICU patients. Participants will be screened for their sedation status daily as well as pre- and post-drug or placebo administration as indicated in table 3 above.

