4-a-6.11) Serum Drug Levels: Daily blood samples will be collected to determine lorcaserin serum levels by a LC-MS/MS assay and pharmacokinetics. The serum drug samples will be collected and run in at least 2 batches, with the first batch run on specimens after randomization of at least the first 3 patients to lorcaserin (will be done without unblinding the research team regarding the study ID of these subjects). The peak plasma concentration after oral dosing is 1.5 to 2 hours. However, feeding can increase the peak plasma time by 1 hour. Thus, peak concentration samples will be collected at 2hours \pm 15 minutes for NPO patients and at 3 hours \pm 15 minutes for fed patients. Lorcaserin has a plasma half-life of about 11 hours, and trough concentration samples will be collected at approximately two half-lives, or 24 hours \pm 30 minutes.

4-a-6.12) Electromyography (EMG) and Nerve Conduction Studies (NCS):

Nerve conduction will be assessed via the following screening nerve conduction studies in participants after enrolment, to detect potential peripheral neuropathy. NCS results will help us interpret the results of strength tests.

- Motor NCS of bilateral peroneal nerves
- Motor NCS of unilateral ulnar nerve. If ulnar neuropathy at the elbow is diagnosed (slowing of ulnar conduction velocity across the elbow to below 35 m/s or a drop in ulnar motor amplitude of >50% with stimulation above the elbow), Motor NCS of the ulnar nerve of the other extremity will be performed as well.

- Sensory NCS of unilateral ulnar and sural nerves

Motor unit recruitment rate will be assessed via the following EMG studies as well

- EMG of unilateral vastus lateralis muscle
- EMG of unilateral deltoid muscle

If EMG and NCS studies have already been done for clinical purposes, they will NOT be repeated for research purposes, and the pre-existing results will be used for research purposes.

4-b) Study duration and number of study visits required of research participants.

Each participant regardless of group, will be in the study for two 2-day blocks. The detailed timeline of events are detailed in Table 3.

4-c) Blinding, including justification for blinding or not blinding the trial, if applicable.

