 - ii. If the dosage of any interacting agent (e.g., analgesic) is routinely titrated for desired clinical effect, the clinical team will be informed and cautioned to ensure titration occurs with the consideration for potentiation or decrease in the interacting agent's effect.
 - iii. If neither substitution, temporary discontinuation or titration of a potential interacting agent is possible, the patient will be excluded / withdrawn from the study.

4-e) Justification for inclusion of a placebo or non-treatment group.

In our proposed study, patients will be randomized to receive either lorcaserin or Placebo. The FDA-approved drug under study in this trial, lorcaserin, does not have any published data supporting efficacy for muscle weakness in the ICU. Hence, no therapy known to be effective is being withheld from the placebo group. Given that our primary and secondary outcomes are based on semi-objective assessments of muscle strength or subjective assessments of cognitive/psychological symptoms, a control group (with blinded outcomes assessments) is required to reduce bias in patients' outcome assessment. Patients in the control group will continue with routine therapy as deemed appropriate by the clinical team.

4-f) Definition of treatment failure or participant removal criteria.

1. Participants will be removed from this study if the surrogate decision-maker, the patient (when capable of medical decision-making) or the patients' medical team makes a request for removal from the study.
2. As stated in Section 4-d, in the event a participant is scheduled to receive pharmacologic therapies that may potentially interact with the study drug (see appendix A), and substitution, gradual titration or discontinuation of interacting agent is not safe or feasible, within the decision rules outlined in Section 4-d, the participant will be withdrawn from the study.
3. The study drug or placebo will be discontinued for the following physiologic changes. Data collection will continue in these participants.
 1. An increase AST > 8 times the upper limit of normal (ULN)
 2. An increase in ALT > 8 times ULN,
 3. A decrease in creatinine clearance <30 mL/min,
 4. New-onset Q-T prolongation, defined as
 - QTc>500 msec
 - A >60 msec increase in QTc from baseline
 5. New-onset 2nd or 3rd degree heart block without a permanent pacemaker,
 6. Persistent heart rate <60 bpm
 7. New-onset priapism
 8. Serotonin Toxicity (as determined by Hunter Criteria, as previously described)

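### Table 3 schedules no EKG after the 30 mg dose until Day 4, although 4-a-5 says that Day 3 assessments match Day 1

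*Combined protocol and SAP*

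**What the plan says.** Section 4-a-5 gives 10 mg or placebo on Day 1 and 30 mg or placebo on Day 3. For Day 3 it states: "Both groups also will undergo assessments before and after administration of lorcaserin/placebo (identical to Day 1". There is no later dose: "On Day 4, the intervention and control group participants will not receive any lorcaserin/placebo".

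Table 3 sets the schedule, and its title explains that "numbers indicate the number of times within each study day that each measurement is performed". One row reads "Neuro Psychiatric Screen 2 1 1 1" for Days 1 to 4, and the EKG row has the same four counts. RASS, CAM-ICU and the three strength rows read 2, 1, 2, 1. Their 2s carry a triple-asterisk mark, which means one measurement within 4 h of dosing and one 2 to 6 h after it.

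Section 4-a-6.3 asks for daily EKGs and adds: "In particular, this test will be obtained prior to every dose of lorcaserin or placebo". An EKG already done for clinical care is accepted. Section 4-a-6.6 calls the neuropsychiatric screen daily and gives no time relative to dosing.

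On kinetics, 4-a-6.11 says "The peak plasma concentration after oral dosing is 1.5 to 2 hours", about 1 h later when fed, and "Lorcaserin has a plasma half-life of about 11 hours". On action, 4-f item 3 says "The study drug or placebo will be discontinued for the following physiologic changes". Its list includes QTc prolongation, heart block, and new hallucinations or euphoria on the NPI-C.

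**The concern.** Safety in ICU patients is objective 2-1, and 30 mg is both the higher dose and the dose in the primary comparison (7-a). Section 3-f promises adverse-event observations at set intervals after each dose. Section 8-a, item 1 d, links psychiatric effects to short-term studies at supratherapeutic doses.

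A site that follows Table 3 would record no protocol EKG in the hours after 30 mg, and might take the only psychiatric screen of that day before the dose. RASS and CAM-ICU are repeated after dosing, but they measure sedation, agitation and delirium. They do not give QTc or AV conduction, and criterion 10 of 4-f item 3 is defined by the NPI-C. A clean EKG and psychiatric record could then be read as reassurance about 30 mg at peak when nothing was scheduled there.

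**Working it through.** **1. Compare the rows of Table 3.** Eleven rows have daily counts.

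| Rows | Day 1 | Day 2 | Day 3 | Day 4 |
|---|---|---|---|---|
| EKG; neuropsychiatric screen | 2 | 1 | 1 | 1 |
| RASS; CAM-ICU; handgrip; MMT; quadriceps | 2 | 1 | 2 | 1 |
| Chart review; laboratory; Hunter; serum level | 1 | 1 | 1 | 1 |

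Nine of 11 rows agree between Days 1 and 3, and only the EKG and the screen differ. All 11 agree between Days 2 and 4, so the matching statement for Day 4 is accurate. The intact 2, 1, 2, 1 rows make a shifted column unlikely. The Day 3 column heading shows three asterisks where the 30 mg footnote has two. Even if that were the timing mark, a single measurement cannot be both before and after the dose.

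**2. Place the single Day 3 EKG.** Section 4-a-6.3 requires one before every dose. One EKG on a dosing day is therefore the pre-dose one, and the next scheduled EKG is on Day 4.

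**3. Place the single Day 3 screen.** Neither Table 3 nor 4-a-6.6 gives it a time. It may be before or after 30 mg.

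**4. Exposure at the Day 4 EKG.** Inputs: half-life 11 h and peak at 2 h (4-a-6.11). Linear kinetics is assumed, so the 30 mg peak is 3 times the 10 mg peak. The plan gives no exposure figure for the EKG to reproduce. It does call 24 h roughly two half-lives; 24/11 = 2.18, and counted from a 2 h peak it is 22/11 = 2.00.

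Fraction of peak left at t hours = 0.5^((t − 2)/11).

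- t = 24 h: 0.5^2 = 0.25 of the 30 mg peak; × 3 = 0.75 of the 10 mg peak.
- Fed, peak at 3 h: 0.5^(21/11) = 0.266; × 3 = 0.80.
- Half-life assumed 9 h or 13 h: 0.55 or 0.93 of the 10 mg peak.
- Table 3 gives no hour for the Day 4 EKG. At 16 h: 0.414 × 3 = 1.24. At 30 h: 0.171 × 3 = 0.51.
- What is left of the 10 mg dose 72 h after it is 0.5^(70/11) = 0.012 of its peak, which is ignored.

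**5. Exposure in the existing post-dose window.** At 2 h after 30 mg: 3.00 times the 10 mg peak. At 6 h: 0.5^(4/11) × 3 = 2.33 times.

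The first scheduled EKG after 30 mg thus sees roughly 0.5 to 1.2 times the 10 mg peak, against 2.3 to 3.0 times in the window already used for RASS and CAM-ICU.

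**The case against.** The best defence is that the second Day 1 EKG and screen are enrolment baselines, not post-dose checks. Neither row carries the triple-asterisk mark. The text on the EKG and the screen speaks only of daily or pre-dose measurement, while the text on RASS, CAM-ICU and strength says pre- and post-dose. QTc change in 4-f is measured from baseline. Nor can the before-and-after sentence in 4-a-5 cover every row, since chart review, laboratory tests and Hunter are listed once even on Day 1. This stands as to intent. The documents do not show that 30 mg gets fewer post-dose checks than 10 mg, only fewer checks on the day. It does not supply an EKG after 30 mg, and it leaves the statement in 4-a-5 wrong.

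Other points also stand in part. Section 4-a-6.3 notes that ICU patients commonly have an EKG daily, so a clinical one may fall near the peak, but none is required there. The Day 3 screen may follow the dose, and the Day 1 and Day 2 screens would then show whether a symptom is new. Section 3-e reports that doses up to 60 mg were tolerated. The decrease in heart rate in 8-a came from a year-long trial, so it is not evidence of an acute effect of one dose.

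Two stronger readings are tempting. A reader might infer that the gap disables the discontinuation criteria. It does not: 30 mg is the second and last dose, so an EKG 2 h later would also leave nothing to stop. The criteria do work between the doses, and the absence of a trial-level rule in 7-d is a stated choice. A reader might also want a number for missed events. The documents give neither event rates nor the share of effects lasting to Day 4. If all persist, nothing is lost.

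**Conclusion.** The inconsistency holds, and so does its consequence for the EKG: none is scheduled after 30 mg until Day 4, at about 25% of the 30 mg peak (0.75 of the 10 mg peak) at 24 h. That figure rests on the stated half-life, a 2 h peak and assumed linear kinetics; across the clock times tried it runs from 0.51 to 1.24 of the 10 mg peak. For the neuropsychiatric screen the conclusion is weaker: its Day 3 time is undefined, so post-dose cover is uncertain rather than absent.

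The loss is to objective 2-1, in EKG and psychiatric data near peak at the higher dose. Dosing, the primary comparison and the sample size are untouched. This is worth correcting because it is cheap and 4-a-5 already promises it. The text does not reveal which of the two statements the authors meant.

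**What to change.** In Table 3, set EKG and neuropsychiatric screen to 2 on both Day 1 and Day 3, with the triple-asterisk timing (within 4 h before, 2 to 6 h after dosing) that RASS and CAM-ICU already carry. State that a clinical EKG in that window counts under 4-a-6.3. If a single Day 3 check is really intended, correct the claim in 4-a-5 that Day 3 matches Day 1, give the time of the check, and say why one is enough at 30 mg.

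The cost is one extra EKG and one extra screen per participant: with 10 + 5 = 15 participants, at most 15 of each. Assessors are already due in that window for RASS, CAM-ICU and strength, and the peak serum sample falls at about 2 or 3 h. The downside is some incidental EKG findings in both arms. The Hunter row, 4-f and 7-d need no change.
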